2.1 Participant Selection

2.1.1 Total Numbers of Participants, and Study Duration

Randomisation will continue until each arm of the study consists of at least forty-two (42) index cases, plus their households. The study population will also be stratified according to family size. The duration of the study for each participant will be 2 weeks.

2.1.2 Inclusion Criteria

- 1. Males and females, minimum age 4 years, with no upper age limit who are family members of an eligible index case (as defined below).
- 2. People who upon examination, are confirmed to have an active infestation with head lice, as shown by presence of at least one live louse on Day 0 are eligible as index cases. For the purposes of randomisation, only the first presenting case in a household shall be considered a Primary index case.
- 3. People who give written informed consent or, if the prospective participant is under

- 16 years of age, whose parent/guardian gives written informed consent to participate in the study.
- 4. People who will be available for home visits by MEC study team members over the 15 days of the study.
- 5. Primary Index cases should preferably be children between the ages of 5 & 11 years but not adults, although adults may be secondary index cases, and must have at least one sibling of similar age, with at least one responsible adult living under the same roof.

2.1.3 Exclusion Criteria

- 1. Anyone with a known sensitivity to any of the ingredients in Vamousse Lice Defence Shampoo, or The Control Shampoo (see **Section 2.2.1**).
- 2. Anyone with a secondary bacterial infection of the scalp (e.g. impetigo) or who have a long-term scalp condition (e.g. psoriasis of the scalp).
- 3. Anyone who has used a treatment for head lice infestation within the previous 7 days.
- 4. Anyone who has been treated using a trimethoprim-based antibiotic product during the past 4 weeks or who is currently under such treatment.
- 5. Pregnant or breast-feeding mothers.
- 6. Anyone who has participated in another clinical study within 1 month before entry to this study.
- 7. Anyone who has already participated in this clinical study.

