1.1 Summary of the Study

Title: Prevention of infestation with *Pediculus humanus*

capitis in the family group using a pediculicidal shampoo: A prospective, randomised controlled

study.

Chief Investigator: [name]

Study Monitoring: Onorach Limited

Estimated Study Start: January 2022

Estimated Study Finish: March 2022

Participants: Eighty-four (84) participants (the Index Cases) with

evidence of an active head louse infestation and their Households as the unit of randomisation will be recruited

to the study. All Index Cases will be treated with

Vamousse Treatment Mousse. Forty-two (42) participants and their Households will be treated with Vamousse Lice Defence Shampoo and forty-two (42) with The Control Shampoo. All participants will use the randomly assigned shampoo for fourteen (14) days and will be assessed for active head lice infestation at the end of that time.

Type: Eligible children and adults

Products: Vamousse Lice Defence Shampoo and The Control

Shampoo.

Methods of Application:

Both preparations will be applied to wet hair, massaged into the scalp and left in the hair for 3 minutes and no more than 5 minutes before rinsing with water and towel-drying. (see Section 2.3.3.2).

Study Design:

Participants will be recruited into the study by household and randomised to receive either Vamousse Lice Defence Shampoo or The Control Shampoo.

Index cases will be assessed for presence of head lice at their day of recruitment (Day 0) in order to ensure that all participants have live lice present at the start of the study. Other family members who proactively complain of head lice infestation will be treated as though they are an index case. All index cases will be treated the same day with Vamousse Treatment Mousse following confirmation of their eligibility. A member of the Medical Entomology Centre (MEC) study team will apply the treatment. All members of the household will commence using Vamousse Lice Defence Shampoo on Day 0 and will continue to use the shampoo daily for fourteen (14) days.

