On Day 3, the index case will be assessed for lice infestation; if necessary, a second treatment with Vamousse Treatment Mousse will be applied. Index cases with active infestation on Day 3 will be assessed again on Day 6 and treated again if the infestation is still active. All participants will be assessed for the presence of live head lice by dry detection combing on Day 14. No other active assessments will take place during the course of the study. If, however, a member of the household complains of infestation, a member of the MEC team will confirm the presence of live lice and they will be offered treatment with Vamousse Treatment Mousse.

Aims of the Study:

To demonstrate superiority of Vamousse Lice Defence Shampoo to The Control Shampoo in the prevention of lice infestation among close family members.

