1.4 Design in Brief

This trial will be a randomised, parallel group study of a topical treatment for head lice (Vamousse Lice Defence Shampoo) in comparison with a control preparation (The Control Shampoo). At least eighty-four (84) index cases and their households will be recruited, randomised by household and stratified by family size (see Section 3.4 for

details).

At the first visit (Day 0), verbal consent will be obtained to check for the presence of live head lice in the index case, using a fine-toothed plastic detection comb. Any other family member who proactively complains of infestation will also be checked and thereafter will receive treatment as though they are an index case, but will still count as a member of the household. Other household members will not be assessed for the presence of lice.

After the preliminary assessment, participants can be enrolled to the study, provided the index case has an active infestation, all individuals comply with the inclusion/exclusion criteria and any further questions they may have are fully dealt with.

Participants (or their parents/guardians if they are younger than 16 years) will be asked to give written informed consent and sign a Consent Form before participation in the study. There will be a separate Assent Form for children capable of giving written assent. Assent Forms will be witnessed by the parent/guardian and signed by the Investigator.

All prospective index cases who fit the selection criteria (see section 2.1.2 and 2.1.3) will be confirmed as having an active head louse infestation prior to commencement of treatment (see below).

The household of the index cases enrolled on to the study will be randomly allocated to receive one of the two study preparations with at least forty-two (42) individuals allocated to each (see Section 3.4 for details). The Investigator will assign each Initial index case a study number, this being the next available number from a randomised treatment allocation sequence. The treatment allocations will be made double blinded, identified only by a code. Instructions for use will be held in sealed envelopes and will only be opened after consent has been received. Assignment will continue until there are at least forty-two (42) initial index cases in each group.

The population will be stratified according to the following criteria:

Number of children $<3/\ge3$ and number of overt infestations on Day 0 =1/>1.

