2.2 Clinical Supplies and Materials

2.2.1 Physical Forms of the Study Supplies

Vamousse Lice Defence Shampoo:

Ingredients:

| | | %w/w | | | |
|--|---------------------------------------|--------|--|--|--|
| Water | | 55.815 | | | |
| Sodium C14-16 Olefin Sulfonate | | 20 | | | |
| Cocamidopropyl Betaine | | 10 | | | |
| Sodium Cocoyl Isethionate* | | 3 | | | |
| Cocamide DIPA | | 2 | | | |
| Benzyl Alcohol | | 1.5 | | | |
| Butyl Lactate | | 1.25 | | | |
| Citric Acid Anhydrous | | 0.1 | | | |
| Polyquaternium-10 | | 0.25 | | | |
| Tetrasodium EDTA | | 0.1 | | | |
| | Propylene Glycol | | | | |
| Liquid Germall Plus | Diazolidinyl Urea | 0.6 | | | |
| | lodopropynyl Butylcarbamate | | | | |
| | PEG-150 Pentaerythrityl Tetrastearate | | | | |
| Crothix Liquid | PEG-6 Caprylic/Capric Glycerides | 3.5 | | | |
| | Water | | | | |
| Tea Tree Oil | | 0.01 | | | |
| Eucalyptus Oil | | 0.01 | | | |
| Vamousse Shampoo Oil B6160 IV (same as B- 6160 but different fragrance) - Lebermuth | Geraniol | 1.865 | | | |

The Control Shampoo:

Ingredients:

Water SLS

Cocamidopropyl betaine

NaCl

Litchi chinensis Fruit Extract

Cocamide MEA

Cocos Nucifera Oil

Panthenol

Parfum

Glycol Diastearate

Polyquaternium-10

Sodium Benzoate

Citric Acid

Disodium EDTA
Glycerin
Propylene Glycol
Sodium Acetate
Pantolactone
PPG-6
Sodium Hydroxide
Benzyl Alcohol
Coumarin
Limonene
Linalool

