2.3.2 Randomisation

The randomised treatment allocation code will be generated using the free online randomisation service provided at http://www.randomization.com/. The treatment allocation will be made in 22 balanced blocks of 8 treatments, which will provide sufficient numbers for the randomisation allocations together with enough additional allocations as may be required to address any overruns or replacements. The Seed number and date of randomisation will be recorded on the randomisation plan. The randomisation sequence will be held by the packaging company responsible for clinical trial supply and, in order to maintain blinding, will not be revealed to the sponsor, investigators or other study personnel until the end of the study.

The individual treatment allocations will be prepared as sheets bearing the anonymous identification of the product to be used (bottle number) and instructions for application. The product identification/instruction sheets will be sealed in opaque envelopes numbered sequentially on the outside with the participant number taken from the randomisation schedule. Each envelope will be enclosed in a CRF prior to use. Each investigator delegated to enrol participants will allocate the numbered CRFs to participants in numerical sequence. However, where two or more investigators, each allocated separate blocks of numbers, enrol participants in parallel the overall chronological sequence will not necessarily follow the numerical sequence.

Only after written informed consent has been obtained will the investigator allocate a study number and open the randomisation envelope for that number. As detailed above, the envelopes will contain no other information that could compromise blinding. The investigating team will keep a copy of the randomisation code also in a sealed envelope, in case an adverse event, reaction, or any other emergency circumstance necessitates that the code be broken.

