2.3.3 Study Methodology

2.3.3.1 Pre-recruitment

Some participants may be obtained via schools and/or school nurses with whom MEC collaborates in screening for head louse infestation. Primarily recruitment will be via radio advertising. Respondents to advertising will be put in contact with MEC via a "text-back" service. When contact is made, a detailed Participant Information Booklet (PIB) will be provided by post or email to explain the purpose of the study. This will include a children's section explaining what will happen if the person enters the study. It will also contain a General Data Protection Regulation (GDPR) statement relating to protection of the integrity of personal data.

On first contact a member of the study team will conduct a brief interview to establish whether the person(s) will be suitable for entry into the study. If they wish to enter the study, they will be visited and conducted through a consent process, which includes explanation of study procedures and answers to any questions about the study. Potential participants must have had access to the PIB for at least 24 hours before the recruitment visit takes place.

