2.3.3.2 Recruitment (Day 0)

Screening:

Each potential index case will be asked for permission to assess their hair to determine

whether live head lice are present at the start of the study. The assessment will be made by dry combing the hair with a plastic fine-toothed head louse detection comb. Any family member complaining of symptoms of infestation will also be assessed and if confirmed, will be recorded in the CRF. Thereafter, they will receive treatment as though they are an index case. Other family members will not be assessed.

Details will be recorded of how many people share the place of residence with the index case(s).

Consent/Assent:

Potential participants and/or parents/guardians will be asked if they understand the requirements of the study, as set out in the PIB, and if they have any further questions concerning it. Provided they still wish to enter the study and meet the inclusion/exclusion criteria for entry, the participant or parent/guardian (when the participant is below the age of 16) will read and sign the Consent Form. The Investigator will countersign the Consent Form.

A separate Assent Form will be available for those under the age of 16 provided they are capable of signing their name. The Investigator and the parent/guardian will countersign the Assent Forms. A copy of the Consent Form and, if appropriate the Assent Form, will be given to the individual or the carer.

Should an adult member of the household not meet with the inclusion/exclusion criteria, it may not necessarily mean the entire household is ineligible. At the discretion of the investigator, the household may be enrolled and the excluded family member will recorded as a non-participant.

Case Record Form completion:

Personal data allowing identification of an individual will not be recorded in the CRF. However, as there are no source medical documents (i.e. patient medical records) available to the investigators, a Source Data Verification Sheet will be completed for each participant that will be maintained separately from all other study documentation. This Sheet will include information such as name, date of birth, address, and contact details for the General Practitioner. A copy of the GDPR statement covering security of personal data collected during the course of the study will be given to the carer.

The following information will be recorded in the CRF:

- 1. Declaration of Receipt of Informed Consent and GDPR statement:

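### Exclusion criterion 1 covers known sensitivity to the two shampoos, but not to the Treatment Mousse that every index case must receive on Day 0

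*Protocol*

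**What the plan says.** Section 2.1.3, item 1, excludes "Anyone with a known sensitivity to any of the ingredients in Vamousse Lice Defence Shampoo, or The Control Shampoo" and refers the reader to Section 2.2.1. That section, headed "Physical Forms of the Study Supplies", gives ingredients for Vamousse Lice Defence Shampoo and The Control Shampoo and for nothing else.

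The Mousse is a separate product and index cases have no choice about it. Section 1.1 states: "All index cases will be treated the same day with Vamousse Treatment Mousse following confirmation of their eligibility". Section 2.3.3.2 (Procedure) has it applied to dry hair in an amount that saturates hair and scalp, then left for 15 minutes before it is washed off. Section 2.3.3.3 repeats it on Day 3 if live lice are found, and again on Day 6 if they are still there. Under Sections 1.4 and 2.3.3.2, a family member who complains on Day 0 and is confirmed to be infested gets the same treatment.

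Later use is by offer. For a household member who complains during follow-up, Section 1.1 says "they will be offered treatment with Vamousse Treatment Mousse". Section 2.3.3.5 makes a similar offer to anyone with live lice on Day 14.

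Entry turns on the listed criteria. Section 1.4 enrols a household provided, among other things, that "all individuals comply with the inclusion/exclusion criteria", and the case record form (Section 2.3.3.2, item 7) documents that they are met.

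**The concern.** The protocol accepts that a known sensitivity is a reason to keep someone out, and applies that to shampoos left on for 3 to 5 minutes. It gives no reason for leaving out the product that stays on for 15 minutes and that study staff apply themselves. Primary index cases are children, preferably aged 5 to 11 (Section 2.1.2, item 5).

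At stake is whether a child with a known Mousse sensitivity is kept from a compulsory scalp application by a written rule, or only because someone raises the matter on the day.

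**Working it through.** No arithmetic applies. The protocol gives no sensitivity rate and no Mousse ingredient list, and the point depends on no power or sample-size figure. The check is to follow one child through the written steps: a candidate index case known to react to the Mousse and to neither shampoo.

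1. **First contact (Section 2.3.3.1).** A brief interview judges whether the person is suitable for the study. Its content is not specified. It may catch the child, but nothing requires it to.
2. **Consent visit (Sections 2.3.3.1 and 2.3.3.2).** The consent process is one "which includes explanation of study procedures and answers to any questions about the study". A parent may mention the reaction. No rule says what follows if they do.
3. **Criteria (Section 2.1.3).** Item 1 names only the shampoos, so the child passes. Item 2 concerns scalp infection and long-term scalp conditions. Item 3 concerns lice treatment in the previous 7 days. The remaining items cover trimethoprim-based antibiotics, pregnancy or breast-feeding, other studies and earlier participation in this one. None reaches sensitivity to the Mousse.
4. **Case record form (Section 2.3.3.2, items 6 and 7).** Medical history is recorded, and compliance with the criteria is confirmed. Confirmation is correct on the wording, because the child does comply.
5. **Day 0 application (Sections 1.1 and 2.3.3.2).** Eligibility is confirmed, so the Mousse is due the same day. Instructions for use are said to be provided, but their content is not in the protocol.
6. **After exposure (Section 2.3.7).** Withdrawal for an adverse event is possible, but only once the child has been treated.

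Followed as written, the protocol admits this child and has the Mousse applied.

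**Who is already covered.** A child sensitive to an ingredient that the Mousse shares with either shampoo is excluded by item 1. The gap is limited to sensitivities specific to the Mousse. It would be empty if every Mousse ingredient also appeared in one of the shampoos, which cannot be checked from the protocol.

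**When a new exclusion would act.** Under Section 2.3.3.2, consent is signed "Provided they still wish to enter the study and meet the inclusion/exclusion criteria for entry". Under Section 2.3.2, "Only after written informed consent has been obtained will the investigator allocate a study number". A child turned away on a wider criterion 1 therefore leaves before a number is allocated. No allocation is used up, and the decision cannot favour an arm.

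**The case against.** The strongest reply is that several prompts stand between such a child and the Mousse: the first-contact interview, at least 24 hours with the information booklet, the consent discussion, the recorded history, and application by a trained team member rather than by the family. The booklet and the instructions for use are not shown and may carry a sensitivity warning. The scope of criterion 1 is also understandable, since it covers the randomised products, and the Mousse is the standard-of-care treatment common to both arms.

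Much of this stands. It makes harm unlikely, and it limits the claim to what the protocol text says. It does not close the gap, because in that text none of these steps bars entry or treatment. The Mousse may be standard of care, but the protocol still requires it and should say who must not have it.

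Four stronger readings are tempting and are not supported:

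- A reader might infer that nothing at all would stop such a child. The steps above could well do so.
- A reader might take the minimum of 84 index cases as the number at risk. That is everyone routinely treated, not the sensitive group, and the repeats depend on live lice being found.
- A reader might infer that the trial result is threatened. The Mousse is given in both arms and has no part in the sample-size calculation or the primary test.
- A reader might infer that a sensitive sibling due for the Mousse would force out the whole household, since Section 2.3.3.2 allows for an excluded adult. That section does not say that a child's failure must exclude the household, so its allowance needs no rewriting on this account.

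**Conclusion.** The gap in wording is real and certain on the text: the sensitivity criterion omits a product that is compulsory for every index case. Its practical size is small. The number of children with a known sensitivity specific to the Mousse cannot be derived from the protocol and is probably few or none. The concern is participant safety alone, and it justifies an optional amendment, not a condition of starting. It assumes that at least one Mousse ingredient is absent from both shampoos, and that the documents not shown do not already set a bar.

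**What to change.** Three small changes:

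1. Extend Section 2.1.3, item 1, with wording such as: *or, for anyone to be treated as an index case, Vamousse Treatment Mousse or any of its ingredients*.
2. Add the Mousse ingredients to Section 2.2.1, so that staff can apply the criterion.
3. Have the team ask the same question before any later Mousse is given, whether on a complaint during follow-up or on Day 14.

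The cost is one clause, one ingredient list and one spoken question, with no extra visit or assessor. The downside is that an occasional candidate index case is turned away before allocation. Alpha, power and the 42 families per group stay as they are.

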2.2 Clinical Supplies and Materials

2.2.1 Physical Forms of the Study Supplies

Vamousse Lice Defence Shampoo:

Ingredients:

| | | %w/w | | | |
|--|---------------------------------------|--------|--|--|--|
| Water | | 55.815 | | | |
| Sodium C14-16 Olefin Sulfonate | | 20 | | | |
| Cocamidopropyl Betaine | | 10 | | | |
| Sodium Cocoyl Isethionate* | | 3 | | | |
| Cocamide DIPA | | 2 | | | |
| Benzyl Alcohol | | 1.5 | | | |
| Butyl Lactate | | 1.25 | | | |
| Citric Acid Anhydrous | | 0.1 | | | |
| Polyquaternium-10 | | 0.25 | | | |
| Tetrasodium EDTA | | 0.1 | | | |
| | Propylene Glycol | | | | |
| Liquid Germall Plus | Diazolidinyl Urea | 0.6 | | | |
| | lodopropynyl Butylcarbamate | | | | |
| | PEG-150 Pentaerythrityl Tetrastearate | | | | |
| Crothix Liquid | PEG-6 Caprylic/Capric Glycerides | 3.5 | | | |
| | Water | | | | |
| Tea Tree Oil | | 0.01 | | | |
| Eucalyptus Oil | | 0.01 | | | |
| Vamousse Shampoo Oil B6160 IV (same as B- 6160 but different fragrance) - Lebermuth | Geraniol | 1.865 | | | |

The Control Shampoo:

Ingredients:

Water SLS

Cocamidopropyl betaine

NaCl

Litchi chinensis Fruit Extract

Cocamide MEA

Cocos Nucifera Oil

Panthenol

Parfum

Glycol Diastearate

Polyquaternium-10

Sodium Benzoate

Citric Acid

Disodium EDTA
Glycerin
Propylene Glycol
Sodium Acetate
Pantolactone
PPG-6
Sodium Hydroxide
Benzyl Alcohol
Coumarin
Limonene
Linalool

2.2.2 Packaging and Labelling

Packaging – both preparations

The product will be packed in plastic bottles with each container holding 400mL of material. The bottles will be made from polyethylene terephthalate (PET) containers.

Labelling – both preparations:

The bottles of both preparations used in the study will be numbered and weighed on calibrated scales before use. A clinical trial label will be affixed identifying the individual bottle number of the anonymized treatment. A blank section will be provided for completion of Household number and initials of the Primary Index case. Both products will be labelled with appropriate clinical trial labelling that will also state that they are "For Clinical Trial Use Only".

